Short-time behavioural intervention in post-Covid syndrome (SIPCOV): A pragmatic randomised controlled trial

NCT05196451

February 21., 2022

1. Introduction

Persistent post-infectious symptoms (PPIS) after Covid-19, often referred to as *post-Covid syndrome*, may be considered as an epidemic in its own right

The Covid-19 pandemic is an unprecedented threat to health and welfare globally. It is increasingly clear that Covid-19 may result in disabling long-term sequelae often referred to as *post-Covid syndrome* or “*Long Covid*”, being equally common among hospitalized and non-hospitalized patients.^{29,30} Evidence suggests that most post-Covid syndrome cases fit within the label of *Persistent post-Infectious Symptoms (PPIS)*, encompassing chronic fatigue, pain and other symptoms, but with scarce findings on standard clinical examination.^{6,24,27,31}

PPIS is a common sequel after several acute infections with a diverse array of pathogens, ranging from infectious mononucleosis (IM) caused by Epstein-Barr virus, to Q-fever caused by the bacterium *Coxiella burnetii*, and gastroenteritis caused by the parasite *Giardia lamblia*,^{10,12} or as an adverse effect following vaccination.⁹ PPIS is a pathogen-independent phenomenon that phenotypically appears as an abnormal perpetuation of the acute sickness response (ASR), which is a stereotyped collection of physiological, behavioral and psychological manifestations to an infectious event.¹ Across multiple prospective cohort studies, almost one half of subjects report PPIS six months after the infectious event, and 10-15 % satisfy diagnostic criteria for chronic fatigue syndrome (CFS) (often also referred to as myalgic encephalomyelitis (ME)).^{5,10,12,23,28} Although late recovery may occur chronic disability is common, with strong negative impact upon employment prospects and family networks, and with high societal costs.¹³ Given the total number of Covid-19 cases globally (approximately 140 million by April 2021),³⁷ *post-Covid syndrome may be considered as an epidemic in its own right* (Fig. 1).

[figure not shown]

Figure 1. Covid-19 weekly incidence³⁷ and a conservative estimate of post-Covid syndrome prevalence (based on 10 % and 5 % case rate, respectively, 6 and 12 months after the acute infection).¹² Recent evidence suggests that the numbers may be even higher.³⁵

Functional brain alterations may be a central disease mechanism of post-Covid syndrome

The underlying disease mechanisms of post-Covid syndrome remain poorly understood. However, studies of PPIS following other infections have revealed a complex blend of genetic/epigenetic²⁵ and psychosocial⁷ vulnerabilities, in concert with autonomic,^{40,41} hormonal,²² and immunological²¹ alterations.

A prominent model of PPIS consider *functional brain alterations* to be a central pathophysiological element, possibly explaining other documented aberrations.^{11,26,42} This assumption is supported by functional brain imaging studies,^{38,39} clinical trial outcomes,^{17,32} and fundamental neurobiological concepts,^{3,18} and is also intimately related to more comprehensive theories on sustained activation of biological stress responses.^{33,42}

A rehabilitation program aiming to counteract functional brain alterations in post-Covid syndrome may be effective, but has not been systematically studied

If functional brain alteration is important in the pathogenesis of PPIS (including post-Covid syndrome), it is conceivable that mental and behavioural interventions may have a beneficial effect. Indeed, cognitive behavioral therapy (CBT) is of documented value in PPIS following other infections.^{15,17} As for more extensive and multidisciplinary rehabilitation, little is known regarding

efficacy. To the best of our knowledge, no specific rehabilitation program has been systematically studied among post-Covid syndrome sufferers.

1.1 Needs description

The present study addresses urgent needs for the health care services as well as the scientific community

- *Patient treatment.* This project directly addresses a strong need to develop effective treatment strategies for a large patient group suffering from post-Covid syndrome disability. Thus, it significantly improve health care services. Of note, the pragmatic approach ensures strong external validity and generalizability of the results.
- *Relevance and benefit to society.* This project addresses a highly challenging health problem nationally and internationally, which may have substantial negative impact upon employment issues, social security systems, family networks etc.
- *Scientific relevance.* The project addresses a prominent knowledge gap. Also, as the intervention builds upon a specific pathophysiological model, the study results will provide increased insight in disease mechanisms, and may eventually foster similar studies in PPIS following other infections.

2. Hypotheses, aims and objectives

We hypothesise that a short-time outpatient-based rehabilitation program will be beneficial as compared to usual care in post-Covid syndrome

The aim of the present study is to assess the efficacy of a short-time outpatient-based rehabilitation program (the intervention) as compared to usual care (non-intervention) in post-Covid syndrome. The objectives are:

- a) To determine the effect on physical functioning immediately after completion of the intervention. We hypothesises better physical functioning in the intervention group than in the non-intervention group.
- b) To determine the effect on other post-Covid syndrome symptoms (such as fatigue, cognitive difficulties, dyspnoea, pain, sleeping problems) and quality of life (QoL) immediately after completion of the intervention. We hypothesise a beneficial effect of the intervention across all these domains.
- c) To determine adverse effects of the intervention. We hypothesis no differences in the frequency nor seriousness of adverse effects in the intervention group as compared to the non-intervention group.
- d) To determine the effect of the intervention on a long-term basis. We hypothesise that a beneficial effect of the intervention is sustained six months after its delivery.
- e) To explore predictors of intervention effect, including differential effects across subgroups. We hypothesise that time since diagnosis of acute Covid-19 and hospitalization is negatively associated with intervention effect. Furthermore, we hypothesise equal effect of the intervention in the subgroup fulfilling diagnostic criteria for chronic fatigue syndrome/myalgic encephalomyelitis (CFS/ME).
- f) To determine the cost-benefit and cost-effectiveness of the intervention. We hypothesise cost-benefit and cost-effectiveness to be better in the intervention as compared to the non-intervention group.

3. Project methodology

3.1. Project arrangements, method selection and analyses

Design, recruitment, inclusion/exclusion

The proposed study is a 2-arm pragmatic randomised controlled trial (RCT) in which 310 patients who suffer from post-Covid syndrome are randomised to either a short-time outpatient-based rehabilitation program (the intervention) or care as usual in a 1:1 ratio (Fig. 2). Assessments will take

place immediately before randomisation (T0), after intervention or care as usual (T1), and 12 months after T0 (T2). Of note, the timing of T1 will vary in the intervention group, due to the individualized therapy approach (cf. below); T1 in the non-intervention group will be matched accordingly. Patients will be recruited from General Practitioners (GP's) as well as social media and self-referral to the involved institutions, and included based upon the criteria listed in Table 1.

Table 1. Criteria for inclusion and exclusion

Inclusion criteria	Exclusion criteria

Fulfills pragmatic diagnostic criteria of idiopathic post-Covid syndrome (Sandler 2021):
 
 • Confirmed acute Covid-19 by a positive PCR or self-test for SARS-CoV-2. • Persistent symptoms at least 3 months following acute Covid-19 without symptom-free interval. • Functional disability to an extent that interrupts all or a majority of normal activities (such as work/school attendance, physical exercise, social activities, etc.) 	
Other chronic illnesses or demanding life situations that might explain persistent symptoms and disability
 
Sustained organ damage (lung, heart, brain) following acute, serious Covid-19

Age \geq 16 years	Bedridden
Lives in one of the following Norwegian counties: Oslo, Viken, Innlandet, Vestfold og Telemark, Agder	Insufficient command of Norwegian language
Informed consent to participation	

Randomisation and blinding

Patients eligible for the present study are randomized to either intervention or care as usual in a 1:1 probability by a computer-based routine for block randomization; block size will vary randomly between 4 and 6. Allocation will be stratified by severity of illness during the acute stage of Covid-19, operationalized as (1) no admission to hospital, (2) admission to hospital. Allocation concealment will be ensured using sequentially numbered, opaque, sealed envelopes. It is not possible to blind for treatment due to the nature of the intervention. However, during endpoint-evaluation, the responsible researchers will be blinded for group allocation.

Intervention

The intervention consists of an individualized numbers of outpatient encounters (min. 2, max. 8) with medical doctors and physiotherapists at Kysthospitalet. The first meeting is always with a medical doctor. At least one of the encounters has to be face-to-face; the remaining encounters may be organized by video link for patients living far away. The encounters aim to foster a two-stage rehabilitation process:

- Stage 1: This first meeting is with a medical doctor. The intervention aims to eliminate serious pathology with a good anamnesis and clinical examination and to give patients' knowledge and understanding of their condition. The main focus is psychoeducation, based upon the theoretical framework of the Cognitive Activation Theory of Stress (CATS) and the Sustained Arousal-model of PPIS development. These models regard PPIS to be a product of functional brain alterations, which initially are an integrated part of the physiological acute sickness response,¹ but may become inappropriately sustained because of mechanisms such as unconscious expectancies/predictions, worrying tendencies and associative learning processes.^{18,33,34,42} This sustainment causes persistent changes of autonomic nervous activity, hormonal activity and immunological responses, which in turn may explain patients' symptoms and occasional findings (such as high heart rate). Thus, the symptoms and functional disability of patients does not indicate a chronic infectious or autoimmune disorders, and efforts are made to counteract patients' worries.
- Stage 2: The individual follow-up with physiotherapists starts with a repetition of the information given in stage 1, based on patients understanding of their condition and experienced symptoms.

The aim is to counteract patients' worries and subsequent symptom monitoring, and to reassure them that desired activities and graded exercise are both beneficial and safe. Over time, the overall aim is to increase activity levels and normalize activity tolerance by 'uncoupling' an unconscious association between activity and neurobiological stress response activation. The use of both cognitive talking therapy and behavioral modifications (included graded exercise) are important intervention components, and all the health care workers providing the intervention are educated in cognitive behavioral therapy (CBT). Stage 2 is highly individualized based upon the patients' symptom burden and personal preferences. A total of 120 patients' with post-Covid syndrome have received the intervention so far. The number of encounters needed as well as the interval between encounters is highly individual. It is considered important that the number of encounters is based on patients' individual needs, as a fixed number may delay recovery because of unnecessary treatments and result in overuse of health services.

The intervention share some resemblance with Cognitive Behavioral Therapy (CBT) for PPIS.^{15,17} The rationale behind the intervention is explained in detail to the patients' family doctors, ensuring compliant follow-up in primary health care. The cost (in monetary units) will be calculated for both stages of the intervention.

[figure not shown]

Figure 2. Overview of study design.

Effect monitoring

Effect monitoring is primarily based on patient reported outcome measures (PROM), applying a web-based questionnaire composed of several validated instruments. The questionnaire will be distributed to the participants at T0, T1 and T2. It will chart clinical symptoms as well as background, psychological and social variables, and will be used for subgrouping according to different case definitions of CFS/ME. The most important inventories are (cf. appendix 1 for a complete overview):

- *The 36-Item Short-Form Survey (SF-36)* comprises a total of 36 items on subjective mental, social and physical health, which are assigned to 8 dimensions. Scale ranging from 0 (poor quality of life) to 100 (best).^{36,43} The SF-36 instrument was recently recommended as a useful tool to assess rehabilitation needs in post-Covid syndrome sufferers, and is generally recognized as a valid and reliable measurement for intervention trials.²⁰
- *The Chalder Fatigue Questionnaire (CFQ)* charts subjective experience of physical and mental fatigue. In this study, the CFQ total linear score (i.e. the sum across all 11 items, each item scored on a zero to three Likert scale) will be applied. Furthermore, fatigue caseness is defined as a CFQ total dichotomous score of 4 or higher (each item scored 0-0-1-1).
- *The Hospital Anxiety and Depression Scale (HADS)* is a validated questionnaire for charting symptoms of depression and anxiety. It consists of 14 items rated zero to three on Likert scales, allowing computation of sub-scores for depression and anxiety symptoms. In the present study, these sub-scores as well as total sum score will be applied.
- *Adverse effects:* A self-invented questionnaire will address possible adverse effect related to the intervention.

In addition, employment status, usage of social security-systems (i.e. short and long-term sick leave), and usage of health care services (i.e. the number of GP and specialist contacts, hospitalisations, medications, usage of rehabilitation services, etc.) will be charted through register linkage (cf. below) as well as questionnaires to the study participants.

Unexpected findings of other health problems

The questionnaire may reveal unexpected findings of other health problems, such as serious depressive symptoms, substance abuse, etc. We will implement Standard Operating Procedures to ensure that such health problems are identified and that appropriate measures are instituted, such as immediate notifying of the patient's general practitioner/family doctor.

Linkage with health registries

In order to explore predictors of intervention effects (point 2.e), above), linkage with existing health registries will be considered, such as 'Norsk pasientregister', 'Mor-Barn-studien', 'Vaksine-registeret Sysvak', 'Reseptregisteret', 'Intensivregisteret' og 'Pandemiregisteret'. Also, previously recorded medical information from hospital and family doctor records will be exploited for the same purpose. A primary prediction analyses will use the following variables, based upon previous evidence from other studies of PPIS:^{10,12,23}

- *Previous infectious diseases:* COVID-19 diagnosed by PCR-test (date, genetic variant), other infectious events one year prior to inclusion
- *Previous immunizations:* Vaccination against COVID-19 (date(s), type(s)), other vaccinations one year prior to inclusion.
- *Previous and current medical history:* Diagnoses of other chronic diseases, current medication
- *Severity of acute COVID-19:* Hospitalization (days), intensive care unit admission (days), respiratory support, cardiovascular support, neurological sequels, thromboembolic events, immunological and infectious markers during hospital stay (CRP, viral replication numbers).

Other possible predicting factors, such as genetic traits, will not be explored under the current protocol.

Population and sample size calculation

As of July 2021, a total of approximately 103,000 Covid-19 cases have been reported from the geographical areas (five Norwegian counties) from which patients are recruited to the present study. Assuming a 5 % case rate of post-Covid syndrome (cf. Figure 1) of whom 1/5 is eligible and willing to participate, a total of 1,300 patients could potentially be included.

The SF-36 subscale Physical Functioning (SF-36-PFS) will serve as the primary endpoint in the present study. A difference of 10 points is considered clinically significant.⁴³ Similarly, in a study of CFS/ME which shares similarities with post-Covid syndrome, the minimally clinically important difference of SF-36-PFS was reported to be 10.⁴ The scatter of SF-36-PFS scores among post-Covid syndrome sufferers are unknown, but two large Norwegian surveys reported a Standard Deviation (SD) of 20 across all age groups.^{8,14} If SD is set to be 25 in the population under study, and assuming 20 % drop-out rate, the study should aim to *include a total of 310 participants*. This yields a power of 90 % ($\alpha=0.05$) to detect a small to medium effect size.

Statistical analyses

The ‘full analysis set’ (all randomized participants) will be used for intention-to-treat analyses of efficacy. Missing values will be imputed applying multiple imputation techniques. The ‘per protocol analysis set’ is defined as all patients in the ‘full analysis set’ that completed the treatment period without any of the following protocol deviations: Interruption of therapy; Lost to follow-up; Primary endpoint measurements missing; Diagnosed with another chronic disorder during the study period; Experiencing a severe illness or trauma during the study period; Commencing other treatment for post-Covid syndrome during the study period.

Variables will be reported with parametric or non-parametric descriptive statistics, eventually frequency tabulation, as appropriate. General linear models (ANCOVA) will be used for analyses of treatment effect; the baseline values of each efficacy endpoint will be included as covariates. For each statistical analysis, the net intervention effect (the mean change in the intervention group minus the mean change in the usual care group) will be calculated from the parameters of the fitted general linear model and reported with 95 % confidence interval. All statistical tests will be carried out two-sided. A p-value ≤ 0.05 is considered statistically significant. Safety data will be summarized descriptively through appropriate data tabulations and descriptive statistics. No interim analysis will be carried out. A statistical analysis plan will be developed.

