## 2. POWER CONSIDERATIONS

For the SF-36-PFS score (primary endpoint), a difference of 10 points is considered clinically significant. Similarly, in a study of CFS/ME which shares similarities with post-Covid syndrome, the minimally clinically important difference of SF-36-PFS was reported to be 10. The scatter of SF-36-PFS scores among post-Covid syndrome sufferers are unknown, but two large Norwegian surveys reported a Standard Deviation (SD) of 20 across all age groups. If SD is set to be 25 in the population under study, and assuming 20 % drop-out rate, the study should aim to **include a total of 310 participants**. This yields a power of 90 % ( $\alpha=0.05$ ) to detect a small to medium effect size.

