#### **Analyses of intervention effect**

Intention-to-treat analyses (full analysis set) will be used to compare the group allocated to intervention with the group allocated to routine follow-up using general linear models (ANCOVA) for the primary endpoint. Analogous methodology within the generalized linear method group of statistical modeling will be used for secondary endpoints that are not linear. The baseline values of each efficacy endpoint as well as stratification variable will be included as covariates. The null hypothesis is no differences in efficacy variables between the two treatment allocation groups. For each statistical analysis, the net intervention effect (the mean change in the intervention group minus the mean change in the routine follow-up group) will be estimated from the parameters of the fitted model and reported with 95 % confidence interval. An identical methodological approach will be applied for per protocol analyses based upon the per protocol analysis set.

Safety data will be summarized descriptively through appropriate data tabulations and descriptive statistics. No interim analysis will be carried out.

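### Does the stated 90% power fail to follow from 310 randomised patients, a 10-point difference, SD 25 and 20% drop-out?

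*Protocol*

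**What the plan says.** Protocol 3.1 (Population and sample size calculation) and SAP section 2 give the same justification. For the SF-36 Physical Functioning subscale, "a difference of 10 points is considered clinically significant". The scatter in post-Covid patients is said to be unknown, and two Norwegian surveys are cited for an SD of 20. Then: "If SD is set to be 25 in the population under study, and assuming 20 % drop-out rate, the study should aim to" include 310 participants. The resulting 90% power is described as power "to detect a small to medium effect size". Neither document puts a number on that phrase, names a formula or gives a baseline-to-follow-up correlation.

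The analysis is adjusted for baseline. The Protocol states: "General linear models (ANCOVA) will be used for analyses of treatment effect; the baseline values of each efficacy endpoint will be included as covariates". SAP section 4 adds the stratification factor: "The baseline values of each efficacy endpoint as well as stratification variable will be included as covariates".

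The same Protocol subsection estimates the recruitment pool. From about 103,000 reported cases and a 5% case rate, "of whom 1/5 is eligible and willing to participate, a total of 1,300 patients could potentially be included".

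**The concern.** Ten points is the only difference the sample size text mentions, and it stands in the paragraph that ends with 310. A reader will naturally combine it with SD 25, get d = 0.40, and find that 310 randomised with 20% lost does not give 90% in a two-sample comparison. If that reading is right, the type II error for the primary endpoint is about 12% and not 10%, and the trial is about 20 patients short of its own target. The verbal effect-size band does not settle the matter, because it fixes no difference. The recruitment product a few lines earlier is also wrong on its face, which makes the arithmetic around it look less reliable.

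**Working it through.** Inputs:

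- Alpha: "A p-value ≤ 0.05 is considered statistically significant"; sidedness: "All statistical tests will be carried out two-sided" (Protocol 3.1, Statistical analyses).
- SD 25, drop-out 20%, N = 310, 1:1 allocation (Protocol 3.1; SAP sections 1 and 2). Evaluable: 310 × 0.8 = 248, or 124 per arm.
- Difference of 10 points as the powered target: an inference, not stated. d = 10/25 = 0.40.

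**1. What difference gives the plan's 90%?** With 124 per arm, (1.960 + 1.2816) × 25 × √(2/124) = 10.29 points (d = 0.412). With the t distribution it is 10.33 points (d = 0.413). So 310 and 90% agree with each other at about 10.3 points.

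**2. Power at exactly 10 points, unadjusted.** 10 / (25 × √(2/124)) = 3.150, and 3.150 − 1.960 = 1.190, which gives 88.3%. The t-test gives 88.0%. The shortfall is 1.7 to 2.0 points.

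**3. N for 90% at 10 points, unadjusted.** 2 × (1.960 + 1.2816)² / 0.40² = 131.3, so 132 per arm (133 by t-test). Then 264/0.8 = 330, or 266/0.8 = 332.5, rounded up to 333.

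**4. Other routes to 310.** Multiplying by 1.2 in place of dividing by 0.8 gives 264 × 1.2 = 316.8, so 317. Ignoring drop-out (155 per arm) gives 93.9% by t-test. One-sided alpha gives 93.4%, but the tests are two-sided. None of these gives both 310 and 90% at exactly d = 0.40.

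**5. Power of the planned test.** ANCOVA on baseline replaces the SD by 25 × √(1 − ρ²), where ρ is the baseline-to-T1 correlation. The documents give no ρ, so the values below are assumptions (10 points, 124 per arm, t distribution):

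| ρ | Power |
|---|---|
| 0 (unadjusted) | 88.0% |
| 0.2 | 89.3% |
| 0.25 | 90.0% |
| 0.3 | 90.8% |
| 0.5 | 95.2% |

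The break-even ρ is 0.252 (t) or 0.236 (normal).

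**6. Sensitivity to the SD, unadjusted t-test at 10 points.** SD 20 gives 97.5%, 24 gives 90.5%, 25 gives 88.0% and 28 gives 80.0%. An SD of 10/0.4133 = 24.2 gives exactly 90%.

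**7. Recruitment pool.** 103,000 × 0.05 = 5,150, and 5,150/5 = 1,030. The printed 1,300 would need 1,300 × 5/0.05 = 130,000 cases. The ratio to the target is 1,030/310 = 3.3.

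**The case for a change.** The strongest case for a correction is that the sample size text offers one difference and one SD, and no unadjusted route from them arrives at both 310 and 90%. Nor does the verbal band rescue the figure. If it is read as d = 0.2 to 0.5 (an assumption), power with 124 per arm runs from 35% to 98%, so almost any claim would fit it. ANCOVA might restore the 90%, but neither document states or uses a correlation, so it cannot be assumed to be where 310 came from. A change of wording would cost almost nothing, and the recruitment product is wrong without any inference.

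Part of this stands. The powered difference and the method are not stated, so a reader cannot reproduce the 90% without guessing, and the 1,300 does not follow from its factors.

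The step to an error in the stated power does not stand. It needs 10 points to be the powered difference, which neither document says. It also judges the claim by an unadjusted comparison, which is not the planned analysis. Replacing the 90% by 88% for an unadjusted test of 10 points would write into both documents a target and a test that they do not say were used. The figure of 330 against 310 is not a second discrepancy. It is the same 2 points of power expressed as patients.

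**Conclusion.** The arithmetic behind the concern is right, but it does not show that the stated power is wrong or that the trial is underpowered. On the least favourable reading, with 10 points as the target and no baseline adjustment, power is about 88% instead of 90%. That gap closes with a difference of 10.3 points, an SD of 24.2 or a baseline-to-T1 correlation of about 0.25. The SD of 25 is itself a chosen value for a quantity the documents call unknown, set above the surveys' 20. The uncertainty in that one input moves power far more than 2 points.

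What remains is missing detail about which difference and formula lie behind the 90%, and a clerical slip in the recruitment pool. The slip enters no power calculation and leaves feasibility intact. The sample size, endpoint, model and alpha would be the same whichever reading is correct. The effect will be reported with a 95% confidence interval, so its precision can be judged without the planning figure. No change to the plan follows. The conclusion rests on the planned baseline-adjusted ANCOVA being the primary analysis; the correlation values are assumptions, not figures from the documents.
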